## 12.2 Sample Size Determination

The sample size was determined by the maximum number of subjects which could be randomized given the budgetary constraints of the grant funding. It was determined that a total of ten patients per group was financially feasible, thus a total of 40 patients will be enrolled in this study in approximately 1 year.

Enrolling the projected 40 subjects in 1 year is feasible, as the ophthalmology department sees approximately 275 glaucoma patients weekly. Due to the high volume of the glaucoma clinic, the study team should be able to easily recruit their target. Additionally, the study team is comprised of multiple

investigators and research assistants who have been delegated tasks on this protocol which can provide full-time recruitment coverage.

### 12.3 Statistical Methods

A variety of statistical analysis will be used to analyze the results. A paired t-test will be the primary method of analysis. Any significant differences measured will be between the pre and post intervention, with the patient serving as their own control. However, the analysis will not be limited to a paired t-test and will also likely include ANOVA, chi-squared, p-value, linear regression, among others. Other outcomes such as length of time until completion of drops will also be measured and compared to no drop aid controls. Significant differences will be measured with similar statistical analysis as stated previously. Satisfaction of use will be measured with a survey and results will be averaged among those in the same cohort. Any significant differences will also be measured with similar statistical analysis stated previously.

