## 4 Objectives

### 4.1 Study Objectives

The primary objective of this study is to compare efficiency of various drop aids for glaucoma medications objectively via changes in intraocular pressure. The different drop aids that are utilized are the Simply Touch Eye Drop Applicator, the Fabrication Autodrop Eye Drop Guide, and the Owen Mumford OP 6100 Autosqueeze. The central hypothesis is that the use of a drop aid device increases efficiency of glaucoma medication when comparing changes in intraocular pressure.

A secondary objective of this study is to evaluate how often a patient missed their eye when instilling drops with various drop aids in order to assess whether drop aids can decrease medication waste, increase medication compliance, and improve visual function. Additionally, the study will analyze how satisfied the patient is with their drop aid and the likelihood they would continue to use one outside of the study. These satisfaction means will be evaluated with a patient satisfaction survey approximately 3 weeks and 6 weeks after enrollment.

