#### 4.2.1 Primary Outcome Measures

The objective of this study is to compare efficiency of various drop aids for glaucoma medications objectively via changes in intraocular pressure.

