### 5 Study Design

This interventional clinical trial is a prospective, single center, randomized controlled study. Patients being treated for their glaucoma at BMC's Yawkey Eye Clinic will be selected. Patients will be randomly placed, without manipulations by the principle investigator or any member of the research team, on one of the drop aid devices (including Fabrication Autodrop Eye Drop Guide, Simply Touch Eye Drop Applicator, Owen Mumford OP 6100 Autosqueeze), in addition to a no drop aid control, for a total of 4 groups.

Subjects have an equal chance of being randomized to one of the following study arms:

- Arm A: No intervention – Control
- Arm B: Active Comparator- Eye Drop Aids Including:
  - Simply Touch Eye Drop Applicator
  - Fabrication Autodrop Eye Drop Guide
  - Owen Mumford OP 6100 Autosqueeze

The primary endpoint is the comparison of baseline IOP measurement and follow-up IOP measurement. This comparison will determine the efficacy of using a drop aid. The secondary endpoints include the precision of the drop aid, patient satisfaction, and their likelihood to use a drop aid outside of the study. Data collection for assessment of study objectives will be obtained via standard of care clinic visits and completion of study diary and satisfaction survey by the patient with assistance of research team, if needed.

See the Appendix section 15.1 for a schematic of the study design and section 15.3 for drop aid labels and instructions.

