## 12 Statistical Plan

### 12.1 Study Hypotheses

#### 12.1.1. Primary Objective: Intraocular Pressure

Formal hypothesis: Drop aids will be cost-effective in delivery of ophthalmic medications by improving baseline IOP measures to six week visit.

Testable hypothesis: Patient baseline IOP measures will be a statistically significant improvement in accordance to the usage of a drop aid device.

Null hypothesis: The patients, who are assigned to a drop aid device baseline IOP measures will not have a statistically significant change with the usage of a drop aid device when compared to patients not assigned to a drop aid device.

Alternate hypothesis: Patients not assigned to a drop aid device will result in larger significant change when compared to patients who are assigned to a drop aid device.

$$H_0: \mu_0 < \mu_d - \delta$$

$$H_A: \mu_0 \geq \mu_d - \delta$$

Where  $\mu_0$ , is the true mean IOP change from baseline to the six week visit without the drop aid device,  $\mu_d$  is the true mean IOP change from baseline to the six week visit with the drop aid device.

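### The primary IOP analysis is a within-patient pre/post paired t-test, so it does not test the device-versus-no-device hypothesis

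*Combined protocol and SAP*

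**What the plan says.** Section 12.3 (Statistical Methods) names a paired t-test as the primary method and fixes its contrast: "Any significant differences measured will be between the pre and post intervention, with the patient serving as their own control". It adds that "the analysis will not be limited to a paired t-test and will also likely include ANOVA, chi-squared, p-value, linear regression, among others". Its only explicit comparison with the control arm is for something other than IOP: "Other outcomes such as length of time until completion of drops will also be measured and compared to no drop aid controls".

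Section 5 (Study Design) defines the primary endpoint as baseline against follow-up IOP and says: "This comparison will determine the efficacy of using a drop aid".

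Section 12.1.1 poses a different question. Its null hypothesis concerns IOP change in device patients "when compared to patients not assigned to a drop aid device". Its formula sets mean change without a device (μ0) against mean change with one (μd): H0: μ0 < μd − δ, HA: μ0 ≥ μd − δ. The worded alternate reads "Patients not assigned to a drop aid device will result in larger significant change". Section 4.1 says: "The central hypothesis is that the use of a drop aid device increases efficiency of glaucoma medication when comparing changes in intraocular pressure". Section 4.2.1 gives the aim as to "compare efficiency of various drop aids for glaucoma medications objectively via changes in intraocular pressure".

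**The concern.** The trial randomises patients to a no-device group so that IOP change with a device can be judged against IOP change without one. The named primary test looks only at whether IOP moved within patients. A significant fall among device users does not show that they did better than controls.

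A movement in all arms is plausible. Every patient keeps a diary (9.2) and receives the three-week survey call, controls included (9.3.1). Being observed may change how drops are taken, and IOP varies between visits. A common fall would look like device efficacy; a common rise could mask it.

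Running a paired test in each arm and comparing which reach significance does not help, because that is not a test of the difference between arms. Section 12.3 also leaves open whether the devices are pooled or tested one at a time.

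**Working it through.** **Inputs.** Ten patients per group (12.2) and four groups (section 5): 4 × 10 = 40, which reproduces the stated total and gives 30 device patients and 10 controls. Section 12.2 sets the size by budget, so there is no power figure to reproduce. Section 12.3 states neither significance level nor sidedness; two-sided 5% is assumed. The documents give no SD, expected shift or baseline/follow-up correlation, so shifts are in units of the SD of IOP change, over an assumed range.

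**False-positive rate of the planned test.** Let the device effect be zero and every arm, control included, have mean change c. The paired t statistic on n patients is then noncentral t with n − 1 df and noncentrality c√n. For n = 30 and c = 0.5 the noncentrality is 0.5 × √30 = 2.74. The chance of exceeding the two-sided 5% limits is:

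| Common shift c (SD of change) | 30 pooled device patients | One device arm, n = 10 | At least one of three device arms |
|---|---|---|---|
| 0 | 0.050 | 0.050 | 0.143 |
| 0.2 | 0.185 | 0.088 | 0.241 |
| 1/3 | 0.423 | 0.157 | 0.401 |
| 0.5 | 0.754 | 0.293 | 0.647 |

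The last column is 1 − (1 − p)³, with p from the n = 10 column. Simulation of 100,000 trials at c = 0.5 gave 0.755 (n = 30) and 0.295 (n = 10), in agreement.

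**False-positive rate of a between-arm test.** A shift common to both arms cancels. For 30 versus 10, zero device effect, an assumed correlation of 0.6 and the same four shifts, simulation gave:
- two-sample t-test of change: 0.050, 0.049, 0.051, 0.048 (20,000 trials each)
- ANCOVA: 0.046, 0.055, 0.049, 0.047 (10,000 trials each)

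**What a between-arm test can detect.** The two-sample t-test has noncentrality d / √(1/n1 + 1/n2) on n1 + n2 − 2 df.
- 30 versus 10: power is 27%, 52% and 76% at d = 0.5, 0.75 and 1.0 SD; 80% power needs d = 1.05 SD.
- 10 versus 10 (one device against control): 80% power needs d = 1.32 SD.
- ANCOVA has variance (1 − r²) / (2(1 − r)) relative to the change score: 0.75, 0.80 and 0.85 at r = 0.5, 0.6 and 0.7. For 30 versus 10 the detectable difference becomes 1.05 × √0.75 = 0.91, 1.05 × √0.80 = 0.94 and 1.05 × √0.85 = 0.97 SD.

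**The hypothesis itself.** Put μ0 = μd into HA: μ0 ≥ μd − δ. It reduces to δ ≥ 0. Section 12.1.1 gives δ no value, and for any δ ≥ 0 the case of no device effect lies inside the alternative. If larger change means larger IOP reduction, the worded alternate also favours no device, against section 4.1.

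**The case against.** The strongest reply is that 12.3 should be read with 12.1.1, which defines the control-arm mean. ANOVA and linear regression are on the list of methods, and the word also in the sentence on other outcomes could imply that IOP is compared with controls too. This shows that a between-arm IOP analysis is possible, not that it is planned. It is only likely, has no outcome, factor or contrast, and is not the primary method.

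The error rates depend on the assumed shift. The plan limits some sources of drift: at least two months on the same medication (7.1, 7.2), no IOP threshold for entry, and withdrawal when the regimen changes (9.4, 10.4). That stands, so the figures are illustrative. They are also two-sided. At zero shift the favourable-direction rate is 2.5% per test and 1 − 0.975³ = 7.3% for any of three arms, and the 14% in that row comes from multiplicity, not from the missing control.

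The direction of the hypothesis depends on an undefined sign. If change is follow-up minus baseline, μ0 above μd favours the device, and the formula, leaving δ aside, points the intended way. The wording and the formula then disagree with each other, so repair is needed either way.

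Two further caveats hold. Section 5 could be read as an equal chance of Arm A or Arm B (20 versus 20, detectable difference about 0.91 SD), although ten per group in four groups gives 30 versus 10. The detectable differences assume that all 40 patients complete.

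**Conclusion.** The concern holds and must be fixed. The named primary test does not test the stated primary hypothesis, and no section specifies a between-arm test of IOP. This conclusion needs no numerical assumption.

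The size of the consequence does. The range of 19% to 75% in pooled device patients rests on normal data, complete follow-up, a two-sided 5% level and assumed common shifts of 0.2 to 0.5 SD. With no shift at all, the pooled paired test keeps its 5% level but still does not estimate the difference between device and no device. The undefined sign of change and undefined δ are further defects to correct at the same time.

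**What to change.** - **12.3:** make the primary analysis a comparison of follow-up IOP between randomised groups, adjusted for baseline IOP (ANCOVA). A two-sample test of change would also answer the question, less precisely. State the level and sidedness, and report the difference with a 95% CI. Keep within-arm paired t-tests as descriptive.
- **Contrast:** name one primary contrast in advance, for example pooled devices versus control, which matches 12.1.1. Each device versus control could be secondary with multiplicity adjustment (for example Dunnett), and device versus device exploratory. As sections 4.1 and 4.2.1 speak of comparing various drop aids, the objective should be aligned with the choice made.
- **Section 5:** define the endpoint as the difference between arms in IOP change from baseline, and make the allocation agree with 12.2.
- **12.1.1:** define the sign of change, correct the worded alternate, and drop or define δ; for example H0: μd = μ0 against HA: μd ≠ μ0.

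The cost is an amendment to wording; IOP is already measured at both visits in every arm. The downside is a result that will look less favourable, with 80% power only for differences of about 0.91 to 1.05 SD (30 versus 10, with or without adjustment). That is a reason to report an honest estimate and interval, not to test a different question. The change does not remove contact that only device patients receive, such as the reinforcement of drop-aid use scheduled at the three-week call (15.1).

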## 2 Protocol Summary

Title:	Glaucoma Drop Aid Study
Population:	Male and Female patients of Boston University Eye Associates, 18 or older, having been receiving the same topical medication for treatment of glaucoma for a minimum of two months
Intervention:	Control: 
 
No Glaucoma Drop Aid Device
 
 Drop Aid Devices: 
 
Simply Touch Eye Drop Applicator
 
Fabrication Autodrop Eye Drop Guide
 
Owen Mumford OP 6100 Autosqueeze
 

Objectives:	To determine the efficacy of drop aid devices for improving medication compliance, visual function, and decreasing medication waste for patients at BMC
Design/Methodology:	Arm A: No intervention- Control Arm B: Active Comparator- Eye Drop Aids  Participants will be randomly assigned into one of the study arms. If placed into Arm A, no drop aid device will be assigned. If placed into Arm B, participants will be assigned one of the three drop aid devices (Simply Touch Eye Drop Applicator, Fabrication Autodrop Eye Drop Guide, or the Owen Mumford OP 6100 Autosqueeze).
Total Study Duration:	Approximately 1 year
Subject Participation Duration:	Subject participation length is variable based on appointment wait times and availability. The minimum duration of this study is 6 weeks.

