#### 4.2.2 Secondary Outcome Measures

The following secondary outcomes will also be measured:

1. Number of times a patient missed their eye when instilling eye drops
2. Patient satisfaction responses with treatment arms
3. Intention to use a drop aid long term

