## 10.4 Stopping Rules

A subject will be withdrawn from the study for any of the following reasons but are not limited to:

- Change to eye drop regimen as determined by their SOC provider

- Failure to comply with drop aid instructions
- SAE or UP resulting from the administered study device

The study will be stopped if the PI, [name], determines that the number of AEs, SAE, and/or UPs exceed that of SOC ocular procedures.

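### Section 12.3 compares time to finish a bottle with controls but has no rule for bottles unfinished at diary collection or open at entry, so finished-only analysis understates a true saving

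*Combined protocol and SAP*

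**What the plan says.** **Analysis.** Section 12.3 makes the paired t-test the main method and adds that the analysis "will also likely include ANOVA, chi-squared, p-value, linear regression, among others". On bottle life it says "Other outcomes such as length of time until completion of drops will also be measured and compared to no drop aid controls", and then "Significant differences will be measured with similar statistical analysis as stated previously". No time-to-event method is named and no censoring rule is given.

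**Data.** Section 4.2 asks for the date each bottle was begun and finished. Section 9.2 asks for the days taken to complete the bottle. The diary in 15.2.3 has three rows, each with one medication name, one start date and one end date. It asks patients to bring their drops to the visit.

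**Timing.** Section 3.2 expects a bottle to last a month and says most patients use two or three medications. Section 2 states "Subject participation length is variable based on appointment wait times and availability" and "The minimum duration of this study is 6 weeks". Section 9.3.2 collects the diary at that final visit. Section 7.1 requires at least two months on the same medication. No section starts a new bottle at randomisation.

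**Status.** Section 4.2.2 opens its list with "The following secondary outcomes will also be measured" and names missed drops, satisfaction and intended long-term use. Bottle life is not on the list and has no hypothesis in 12.1. The objectives in section 2 do include "decreasing medication waste for patients at BMC".

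**The concern.** The methods named in 12.3 for a continuous outcome need a start and an end. A bottle in use at diary collection has only a start. If a device makes bottles last longer, the unfinished bottles are mainly the long-lasting ones in the device groups, so dropping them removes the evidence of a saving.

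A bottle open at entry raises a different problem. Part of it was used before the device was supplied, so its total life mixes use with and without the aid.

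At stake is the dated evidence on bottle life, which bears directly on the waste objective. The error runs toward no difference.

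**Working it through.** **Figures in the plan.** The only sample-size figure is 10 per group × 4 groups = 40 (section 12.2), which reproduces. It was set by budget, and the plan gives no figure for the bottle-life comparison.

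**Can unfinished bottles occur?** With a 30-day bottle (3.2) and the earliest visit at day 42 (6 × 7), a bottle must be opened by day 42 − 30 = 12 to be finished in time. Patients on established treatment will often open their next bottle later than that.

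**Assumptions (not in the documents).** Mean life is 21 days without and 30 days with an aid, a true saving of 9 days, with CV 10%, 20% or 30%. The 70% in 3.2 is a refill threshold, not an observed bottle life.

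**Bottles opened after entry.** Life L is normal with mean m and SD CV × m. The index bottle is opened at time R, where R is uniform on (0, L) for a mid-bottle entry or R = 0 for a new bottle at entry. It counts as finished if R + L ≤ visit day. The apparent saving is the mean L of finished device bottles minus the mean L of finished control bottles (400,000 simulated patients per arm).

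| Start | Visit day | Apparent saving, CV 10/20/30% (days) | Share of 9 days |
|---|---|---|---|
| Mid-bottle | 42 | 8.2 / 6.2 / 4.2 | 47-91% |
| Mid-bottle | 56 | 8.5 / 7.6 / 6.4 | 71-95% |
| Mid-bottle | 70 | 9.0 / 8.6 / 7.9 | 88-100% |
| New bottle | 42 | 9.0 / 8.7 / 7.4 | 82-100% |
| New bottle | 56 | 9.0 / 9.0 / 9.0 | 99-100% |

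For example, 4.2/9 = 47% and 8.2/9 = 91%. At day 42 with a mid-bottle start, 82-93% of control bottles but only 41-46% of device bottles are finished. A repeat run agreed to within 0.1 day.

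**Bottles open at entry.** If a fraction u was used before the device, the device bottle lasts 21u + 30(1 − u) days against 21, so the saving seen is 9(1 − u). With u uniform its mean is 9 × 0.5 = 4.5 days. Simulation, allowing for longer bottles being more likely to be open at entry, gives 4.5-4.9 of 9 days at visits from day 42 to day 84.

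**Other assumptions.** With gamma lives, control mean 30 days, SD 20% of the mean, a new bottle at entry and day 42, true savings of 6, 10 and 15 days appear as 3.9, 5.5 and 6.9. A 6-day saving appears as 5.8 at day 56 and in full at day 84. For bottles open at entry and dated from their true start, 6 days appears as 2.8 at day 42 and 3.1 at day 84.

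**No true effect.** With equal follow-up the finished-bottle difference is within 0.05 days of zero.

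**Diary capacity.** One entry-open and one index bottle per medication needs 2 × 2 = 4 rows for two medications and 3 × 2 = 6 for three. The form has 3.

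**The case against.** The strongest reply is that this is a passing outcome, outside 4.2.2 and 12.1, in a trial sized by budget at 10 per group. That stands and sets the weight.

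A second reply is that the plan never says only finished bottles will be analysed. A reader might infer that 12.3 commits to a finished-only analysis or rules out survival methods. The text supports neither, since its list of methods is open-ended. What stands is that the methods it names cannot use an unfinished bottle and that no section supplies a rule. Section 11.3 requires missing data to be explained, but that governs form completion.

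A third reply is that the size rests on assumed lives and CVs. That also stands. The 47% needs CV 30%, a mid-bottle start and a visit exactly at the protocol minimum.

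Two other inferences fail. Later visits do reduce the bias for bottles opened after entry, but not for bottles already open. The diary also cannot be assumed to hold the needed data unchanged, because three rows may not fit the index bottles of a patient on two or three medications.

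Finally, section 3.2 recognises under-use as well as excess, so a longer bottle life may reflect missed doses. No censoring rule resolves that.

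**Conclusion.** The point holds, with minor weight. The comparison in 12.3 has no rule for unfinished or entry-open bottles, and the protocol's own timing makes both likely. If aids prolong bottle life, analysing finished bottles only understates the saving. On the 21 versus 30 day assumption the loss runs from none to about half, depending on CV, visit date and when the bottle was opened. It can be larger if control bottles already last a month: a 15-day saving appears as 6.9 days (46%) at day 42 in that setting. Counting bottles open at entry shows about half the saving at any visit date.

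A reader might infer that the trial's efficacy conclusion is biased, or that a spurious saving could be reported. Neither follows: IOP does not depend on bottle dates, and with no effect and equal follow-up the difference is essentially zero.

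**What to change.** Add to 12.3:

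> The index bottle is the first bottle of each medication opened on or after randomisation; bottles open at entry are not analysed. A bottle in use at diary collection is right-censored on that date. Each device group, and the pooled devices, are compared with control by Kaplan-Meier curves and a log-rank test, with p-values from permuting whole patients. If a median is not reached, the Kaplan-Meier proportion still in use 30 days after opening is reported. The number per arm with no index bottle is reported. Withdrawn patients are censored at the last date the bottle is known to be in use, and withdrawals are reported by arm and reason.

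Add rows and a still-in-use box to the diary, or allow a second sheet.

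Whole patients are permuted because bottles from one patient are correlated. With two medications, an assumed correlation of 0.5, mean life 30 days in both arms and no effect, the ordinary log-rank test rejects 8.2% of the time and the permutation version 4.8%. With 10 controls against 30 device patients, CV 20%, a mid-bottle start and day 42, power is 96% for the permutation log-rank and 80% for a t-test on finished bottles.

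**Cost.** A few sentences and a small diary edit, with no extra visits or patients.

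**Downsides.**
- Intervals will be wide with 10 per group. In the same setting about 8.7 of 10 control and 13.3 of 30 device index bottles finish by day 42.
- After a mid-bottle start, censoring is mildly informative. The Kaplan-Meier median difference keeps 81-97% of the true value at day 42 and 91-98% at day 56.
- Section 10.4 lists "Failure to comply with drop aid instructions" as a reason for withdrawal, which in practice affects the device groups. Neither 9.4 nor Table 1 says that diaries are collected from withdrawn patients. If 10-30% of device patients withdrew at day 21 and had control-like bottle life (new bottle at entry, visit day 42), censoring them would overstate the median difference by about 3-27%. This should be stated with the result.
- Bottle life should not be read as less waste on its own.

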### 4.2 Study Outcome Measures

The efficiency of various drop aids will be measured through the subject’s glaucoma progression at the end of the study. On the day of enrollment, the subject’s IOP and visual acuity will be measured as part of their standard of care exam. This information is recorded as the baseline exam, and will be compared to measure the patient’s glaucoma progression at the end of the study. Subjects will be required to record the date on which they began each of their glaucoma eye drop bottles, and the date each bottle was finished in a study diary provided by the research team. Subject’s satisfaction will be measured through a brief satisfaction survey approximately 3 weeks after their enrollment. After at least 6 weeks of study participation, subject will be followed up with their regularly scheduled glaucoma provider where they will fill out a second brief satisfaction survey. The study diary will be collected and a routine eye exam will be conducted, with their IOP checked as part of a standard of care clinic visit.

All surveys were created by a member of the research team. The satisfaction survey includes five questions to assess the precision of the drop aid device, overall patient satisfaction, and willingness to use the device long term. The questions are multiple choice questions in which the patient circles the answer that best reflects their response.

Reference Section 12.0 for further statistical analysis explanations.

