### 12.1.3. Secondary Objective: Patient Satisfaction

Formal hypothesis: Drop aid devices will prove greater patient satisfaction than administrations without a drop aid device.

Testable hypothesis: Mean patient satisfaction to those assigned to a drop aid device compared to mean patient satisfaction scores to those not assigned to a drop aid device.

Null hypothesis: Patients assigned to a drop aid device will not show greater patient satisfaction than patients not assigned to a drop aid device.

Alternate hypothesis: Patients assigned to a drop aid device will show greater patient satisfaction than patients not assigned to a drop aid device.

$$H_0: \mu_s < \mu_{sd} - \delta$$

$$H_A: \mu_s \geq \mu_{sd} - \delta$$

Where  $\mu_s$ , is the mean patient satisfaction without the drop aid device,  $\mu_{sd}$  is the mean patient satisfaction with the drop aid device.

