15.2.4 Satisfaction Survey

**Study ID:** \_\_\_\_\_

**Name of study team member completing this form:** \_\_\_\_\_

**Date:** \_\_\_\_\_

**Study Visit:**     3-week phone call         Follow-up clinic visit

1. Do you like the drop aid?
  - a. Yes
  - b. No
  - c. I am not on a drop aid
  - d. I did not use the drop aid
2. Is it easier to instill drops with the help of the drop aid compared without the drop aid?
  - a. Yes
  - b. No
  - c. I am not on a drop aid
  - d. I did not use the drop aid
3. How many times did you miss instilling drops with the help of drop aid?
  - a. None
  - b. 1
  - c. 2
  - d. 3 or more
  - e. I am not on a drop aid
  - f. I did not use the drop aid
4. How many times do you miss instilling drops just using your glaucoma drops?
  - a. None
  - b. 1
  - c. 2
  - d. 3 or more
5. Would you use the drop aid long term?
  - a. Yes
  - b. No
  - c. I am not on a drop aid
  - d. I did not use the drop aid

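### Satisfaction answers are to be averaged, but survey items 1, 2 and 5 mix Yes/No with two non-evaluable options and carry no score, so the mean depends on arbitrary codes

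*Combined protocol and SAP*

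**What the plan says.** Patient satisfaction is the second listed secondary outcome (section 4.2.2). Three sections make a mean its summary:

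- Section 12.3: "Satisfaction of use will be measured with a survey and results will be averaged among those in the same cohort".
- Section 4.1: "These satisfaction means will be evaluated with a patient satisfaction survey approximately 3 weeks and 6 weeks after enrollment".
- Section 12.1.3: the device mean is set against "mean patient satisfaction scores to those not assigned to a drop aid device", and the control parameter "is the mean patient satisfaction without the drop aid device".

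Section 4.2 describes the response format: "The questions are multiple choice questions in which the patient circles the answer that best reflects their response". The form (section 15.2.4) prints letters, not numbers. Items 1 (liking), 2 (ease) and 5 (long-term use) each offer four options: Yes, No, "I am not on a drop aid" and "I did not use the drop aid". Items 3 and 4 ask about misses and offer none, 1, 2, or 3 and above. Item 3 adds the same two non-evaluable options as e and f.

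The survey is completed at the 3-week call and again at the final visit (sections 9.3.1 and 9.3.2), by device and control patients alike. No section gives numeric codes, a rule for the two non-evaluable options, a rule for combining items, or a choice of time point. Chi-squared appears in section 12.3 as a likely method but is not tied to satisfaction.

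**The concern.** A mean needs numbers, and on items 1, 2 and 5 the plan supplies none. Two of the four options say that the question does not apply or cannot be answered; they are not degrees of satisfaction. Whatever value they receive enters the mean as if it were one. If the codes are chosen at analysis, possibly with the data in view, the choice can decide which device looks better.

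Non-use is not a remote case. Section 8 makes this same survey the means of assessing whether patients used the device, so such answers are expected within the device groups. The problem therefore arises among the three devices, before any comparison with control.

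Two related gaps sit beside it. Each patient answers twice and the plan names no analysis time point. And 12.1.3 needs a satisfaction value for controls, which items 1 and 2 cannot provide.

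**Working it through.** **Inputs.** Ten patients per group and four groups (sections 12.2 and 5): 4 × 10 = 40, which agrees with the stated total. That total was set by budget. The documents give no alpha, power or expected value for satisfaction, so there is no satisfaction figure to reproduce. All codings, answer patterns and correlations below are assumptions, and alpha is taken as 0.05 two-sided.

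**1. Ties under printed-order codes (Yes = 1, No = 2, not on an aid = 3, did not use = 4).**
- 7 Yes, 3 No: (7×1 + 3×2)/10 = 1.30.
- 9 Yes, 1 did not use: (9×1 + 1×4)/10 = 1.30.
- More extreme: 6 Yes, 1 No, 3 did not use gives (6 + 2 + 12)/10 = 2.0; 0 Yes, 10 No gives 20/10 = 2.0.
- Over all splits of ten device-group answers into Yes, No and did not use, 30 distinct means are possible, and 21 of them arise from more than one pattern.

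**2. The same data under another coding.** With Yes = 1 and all else = 0, the first pair becomes 7/10 = 0.70 and 9/10 = 0.90. The tie disappears.

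**3. Dependence of the test on the codes.** Take group A with 6 Yes, 1 No, 3 did not use, and group B with 4 Yes, 5 No, 1 did not use:

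| Codes (Yes, No, did not use) | Mean A | Mean B | t-test p |
|---|---|---|---|
| 1, 2, 4 | 2.0 | 1.8 | 0.71 |
| 2, 1, 0 | 1.3 | 1.3 | 1.00 |
| 1, 0, 0 | 0.6 | 0.4 | 0.40 |
| 1, −1, 0 | 0.5 | −0.1 | 0.14 |

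In the first row a low score is favourable, so B looks better. In the last two rows a high score is favourable, so A looks better. The ranking reverses with no change in the data.

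**4. Counter-check.** If only Yes and No are kept, the 0/1 mean is the proportion and recoding changes nothing: 7/10 against 3/10 gives p = 0.081 under either coding. The difficulty comes from the two extra options and the missing rule, not from Yes/No itself.

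**5. Controls.** A control who follows the form picks option c on items 1, 2 and 5. Under printed-order codes every control scores 3 and the group mean is 3.0 with no variation. Under any other coding it is again a constant, and it says nothing about satisfaction.

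**6. Two surveys per patient, only if both were pooled as independent.** With within-patient correlation ρ, the true variance of a group mean is (1 + ρ) times the one assumed. The actual size of a nominal 5% test is 2(1 − Φ(1.96/√(1 + ρ))), a large-sample approximation:
- ρ = 0.5: 0.110
- ρ = 0.7: 0.133
- ρ = 0.9: 0.155

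**7. Precision of the alternative.** Exact (Clopper–Pearson) 95% intervals for the proportion Yes: 6/10 gives 26% to 88%; 18/30, pooling the three devices, gives 41% to 77%. Exact Fisher power for 10 against 10 is 13% for 50% against 80%, 25% for 40% against 80%, and 67% for 30% against 90%.

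**The case against.** The strongest reply is that the authors use the word mean loosely. Section 12.1.4 speaks of mean patients who want or decline long-term use, which reads like shares of Yes and No. If so, the planned statistic may already be a proportion, and the 1.30 tie exists only under a coding that the documents never assign. Section 12.3 also lists chi-squared. This is fair. It turns the point from a wrong calculation into an undefined one. It does not remove it, because even a Yes share needs a rule on whether non-users stay in the denominator, and the sentence on satisfaction itself says averaged.

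Several stronger readings are tempting and should be resisted:

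- *That every survey answer is an unordered category.* Items 3 and 4 are ordered counts with an open top category. They are outside this point, apart from options e and f on item 3.
- *That the plan double-counts patients.* It states when the surveys are collected and is silent on which is analysed; nowhere does it say they are pooled. The 11% to 15.5% error rate is conditional on that step and on an assumed correlation.
- *That proportions would separate the 70% and 90% groups by a test.* At ten per group, 7/10 against 9/10 gives a two-sided Fisher p of 0.58. The gain is an interpretable estimate, not power.

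**Conclusion.** The point holds for items 1, 2 and 5. The planned satisfaction mean has no defined value, and plausible codings of the same answers can tie groups that differ in liking (1.30 each against 0.70 and 0.90) or reverse their order. This rests on at least some device patients answering that they did not use the aid. If none did, and only Yes and No occurred, the device-group mean would be equivalent to a proportion. The codes 1 to 4 are illustrative.

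The missing time point is a real omission, but an inflated error rate cannot be inferred from the text. The device-against-control comparison of mean satisfaction in 12.1.3 cannot be made with this form under any coding.

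This affects a secondary outcome in a 40-patient study sized by budget. It should be corrected, and it does not touch the primary IOP endpoint.

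**What to change.** **Section 12.3.** Replace the averaging with this: for items 1, 2 and 5, report for each device the proportion answering Yes among patients assigned to that device, one answer per patient, taken at the final visit, with an exact 95% interval. Keep patients who did not use the aid in the denominator and show them as their own category. Compare the three devices with an exact test, and report the 3-week answers descriptively. On item 3, options e and f should likewise be reported as separate categories and not scored as if beyond the highest miss count.

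**Section 12.1.3.** Restate the hypothesis as a device-group estimate or a between-device comparison, with no control mean. Align the wording on satisfaction means in section 4.1, and use the same item 5 proportion and denominator in 12.1.4.

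**Cost.** Text changes only, with no new data. The control comparison of satisfaction is given up. Estimates will be imprecise at ten per group (6/10: 26% to 88%), so between-device tests should be read as descriptive support.
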